#### Secondary Endpoints

All secondary analyses, excluding safety endpoints analyses, which will be based on the safety population, and the CRI, which will be based on the per protocol population, will be based on the ITT population. Sensitivity analysis of the primary endpoint and other important endpoints will be performed in the per protocol population, also. The parameters will be evaluated in an explorative manner, providing means, medians, ranges, standard deviations and/or confidence intervals. Rates will be compared using fisher's exact test and continuous variables using t-test. For the time-to-event variable OS, the Kaplan-Meier method will be used, and treatment groups will be compared using a log rank test. All resulting p-values for secondary endpoints will be considered descriptive and will be presented explicitly without referring to hypotheses or a significance level. Usually, no p-value adjustment for multiple-testing will be performed. Thus, the p-values will reflect the comparison-wise error and not the experiment-wise error. All p-values will be two-sided if not stated otherwise. The statistical methods described in this section are suited for the data and distributions usually expected in this type of trials. The suitability will be checked and if necessary, the statistical method will be modified accordingly, with critical discussion of the original and modified results.

Further details of the planned procedures and specific analyses will be defined in the statistical analysis plan, latest prior to locking the database.

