#### 3.6 The relevance of this study to current care and benefit-risk assessment

As elaborated above, the CC patients could benefit from a higher QoL by preserving the subjects' autonomy and ability to self-administer the PN infusions.

Furthermore, CRI represent a serious complication in patients receiving PN, weakens the already impaired subject, potentially delays chemotherapy and thereby diminishes therapeutic success. If the Eurotubes® prove to be efficient in preventing CRI, PN could become safer, more efficient and hospitalization time could be abbreviated.

The procedures used in this study (such as PN application, blood tests, use of a patient's study diary and QoL questionnaires) are in line with the current standard of care or minimal interventional, respectively. 2/3-chamber bags and Eurotubes® used for PN are market-approved infusion units with no experimental approach.

There is no evidence of a negative impact of glucose-reduced nutrition on CC subjects and can therefore be tested for its potential inhibitory effect on tumor growth.

Taken together, the risks emerging from participation in this clinical trial are acceptable, considering the anticipated direct benefits for a subset of patients and the impact of the study results on the future treatment of patients in the given indication.

-CONFIDENTIAL- Page 13 of 33

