#### 5.1.2 Secondary Objectives

#### Secondary Objectives

- To compare the incidence of catheter related infections (CRI) between treatment Arms A and B in the per protocol population.
- To compare the efficacy of PN in terms of body weight, C-reactive protein (CRP) and albumin levels, and overall survival (OS)
- To compare the Quality of life (QoL) by use of the MODIFIED HPN-PROQ questionnaire
- To determine the frequency of PN-related visits by the nursing service
- To compare the safety in terms of the incidence of other catheter related complications, severe, common toxicity criteria (CTC) grade 3-5 infections, and PN-related Adverse Events (AEs)

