#### Secondary Objectives (Arm A-1 vs. A-2)

- To compare the incidence of catheter related infections (CRI)
- To compare the efficacy of PN in terms of body weight, C-reactive protein (CRP) and albumin levels, and overall survival (OS)
- To compare the Quality of life (QoL) by use of the MODIFIED HPN-PROQ questionnaire
- To compare the safety in terms of the incidence of other catheter related complications, severe, common toxicity criteria (CTC) grade 3-5 infections, and PN-related Adverse Events (AEs)

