#### Safety endpoints

- Catheter related infections (CRI) defined as the presence of bacteraemia originating from the intravenous (port) catheter Bacteraemia must be confirmed through a blood culture according to study site-specific routine, preferably through paired quantitative blood cultures or a culture of the catheter if the catheter is removed OR any infections originating from the intravenous (port) catheter, requiring intravenous antibiotics OR infections in the intravenous (port) catheter, requiring intravenous antibiotics or antibiotics delivered to the catheter itself or catheter removal.

  For the diagnostic procedures to be done to confirm CRI, investigators are recommended to follow the DGHO guidelines.
- Catheter related complications such as line occlusions of catheter-related central venous thrombosis;

-CONFIDENTIAL- Page 18 of 33

- Severe, NCI-CTC common toxicity criteria version 5.0 grade 3-5, infections including fever of unknown origin and other Adverse Events according to NCI-CTC common toxicity criteria version 5.0;
- PN-Related Adverse Events (AEs) and hospitalizations during therapy;

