#### Per protocol (PP) population

This population will include all randomized patients who fulfill the inclusion and exclusion criteria and received at least two weeks of PN at home according to treatment arm. Treatment assignment is based on the treatment actually given. Sensitivity analyses of the primary endpoint will be performed on the per protocol analysis set.

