#### Safety analysis set

The evaluation of safety parameters is carried out in the safety population, which is defined as all randomized patients who received at least one application of PN at home. Treatment assignment is based on the treatment actually given.

-CONFIDENTIAL- Page **20** of **33** 

Several subgroup analyses will be performed including but not limited to NRS score, ECOG classification and whether the patient receives concomitant anti-cancer therapy or not. Further details will be specified in the SAP.

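### Catheter-related infection, a safety endpoint, is compared in a per-protocol set that the infection itself can remove a patient from

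*Combined protocol and SAP*

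**What the plan says.** Section 5.2.2 lists CRI first among the safety endpoints. Its definition includes catheter infections "requiring intravenous antibiotics or antibiotics delivered to the catheter itself or catheter removal".

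Section 6.3.1 sets the general rule for safety: "The evaluation of safety parameters is carried out in the safety population", meaning "all randomized patients who received at least one application of PN at home". The per-protocol set is narrower. Patients must meet the eligibility criteria and have "received at least two weeks of PN at home according to treatment arm". Both sets group patients by the treatment actually given.

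Section 6.3.2 (Secondary Endpoints) follows the general rule for safety endpoints but makes one exception, "the CRI, which will be based on the per protocol population". Section 5.1.2 states the same for the main comparison: "To compare the incidence of catheter related infections (CRI) between treatment Arms A and B in the per protocol population". The matching objective for Arm A-1 against A-2 names no population, so the exception in 6.3.2 governs it too.

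**The concern.** Two weeks of home PN is exposure that accrues after randomisation, and a CRI can stop it from accruing. If a CRI ends home PN for good before the two weeks are reached, the patient fails the per-protocol condition and the event goes uncounted. No section exempts patients who stop because of a CRI. Those who continue, or who resume and reach two weeks, stay in; the text does not require the two weeks to be consecutive.

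The safety comparison is therefore conditioned on something the outcome can cause. CRI counts can be understated, and the contrast between arms can be distorted if early CRI-related stopping is more common in one arm. This matters because section 3.6 names CRI prevention as a possible benefit: if Eurotubes "prove to be efficient in preventing CRI, PN could become safer". Readers will look to this result for a safety conclusion about the bags.

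**Working it through.** **The plan's own figures.** The plan gives no rate, power or sample size for CRI, so there is no CRI figure to reproduce. The primary sample size of 128 and 64 does reproduce (80.5% power with the Walters approximation the plan names), but it has no bearing on this point.

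**The definitions.** Take a patient with a first home application on day 1, a CRI on day 9 and no further home PN. The patient is in the safety set (one application is enough) and outside the per-protocol set (less than two weeks). Under 6.3.2 the event is not in the CRI comparison.

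**Illustration of size.** Inputs from the documents:
- Event rates of 4.3 and 8.5 per 1,000 PN days (section 3.4), standing in for Arms A and B. They come from a retrospective review of bloodstream infection with and without additions on the ward, not from home PN or this CRI definition.
- 216 patients at 2:1, so 144 and 72 (sections 4 and 6.1).
- Treatment cap C = 365 days (section 6.2) and window W = 14 days (section 6.3.1).
- PN daily, or 3 days per week (the minimum in inclusion criterion 5).

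Assumed, not in the documents: constant hazards; mean 120 days on home PN apart from CRI (range 60 to 240); a share f of CRIs that end home PN, from 0 to 1, with no resumption.

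Let m = 1/120 per day and l = rate × PN days per week / 7.

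- First CRI by time T: P(T) = l/(l+m) × (1 − exp(−(l+m)T)).
- CRI before W, then stopping before W for another reason: N = (1 − exp(−mW)) − m/(m+l) × (1 − exp(−(m+l)W)).
- Share of patients dropped with a CRI: f × P(W) + (1 − f) × N.
- Per-protocol risk: [exp(−mW)(1−f)(1−exp(−lW)) + exp(−(l+m)W) × P(C−W)] / [exp(−mW)(exp(−lW) + (1−f)(1−exp(−lW)))].

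Arm A, daily PN: l + m = 0.0043 + 0.00833 = 0.01263 and l/(l+m) = 0.3404.
- P(365) = 0.3404 × 0.9901 = 33.7%, and 144 × 0.337 = 48.5 first CRIs.
- P(14) = 0.3404 × 0.1621 = 5.52%, and 144 × 0.0552 = 7.9 dropped if f = 1.
- N = 0.1101 − 0.6596 × 0.1621 = 0.32%, and 144 × 0.0032 = 0.46 dropped if f = 0.

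| PN | f | Dropped, A | Dropped, B | Risk A | Risk B | Ratio |
|---|---|---|---|---|---|---|
| Daily | all treated | – | – | 33.7% | 50.4% | 0.669 |
| Daily | 1 | 7.9 of 48.5 | 7.6 of 36.3 | 33.6% | 50.4% | 0.668 |
| Daily | 0.5 | 4.2 | 4.0 | 35.6% | 53.3% | 0.668 |
| Daily | 0 | 0.46 | 0.44 | 37.5% | 55.9% | 0.671 |
| 3 days/week | 1 | 3.5 of 25.4 | 3.4 of 21.6 | 17.6% | 30.0% | 0.587 |
| 3 days/week | 0.5 | 1.8 | 1.8 | 18.7% | 31.7% | 0.588 |
| 3 days/week | 0 | 0.2 | 0.2 | 19.7% | 33.4% | 0.589 |

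At 3 days per week the all-treated risks are 17.7% and 30.0% (ratio 0.588). With means of 60 to 240 days, the daily-PN counts at f = 1 run from 7.5 to 8.2 (A) and 7.2 to 7.9 (B).

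**Outer limit for distortion.** Give both arms the same true hazard, with f = 1 in one and f = 0 in the other. At Arm A's daily rate the per-protocol ratio is 33.63/37.51 = 0.897 instead of 1. Over both rates and both frequencies, in either direction, it lies within 0.893 to 1.119 at a mean of 120 days, 0.813 to 1.231 at 60 days, and 0.935 to 1.069 at 240 days. This bounds the effect; it is not an expectation.

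**The case against.** The strongest reply is that the comparison hardly changes. With the same stopping share in both arms the ratio stays at 0.668 to 0.671 against 0.669. The per-protocol risk is often higher than in all treated patients (35.6% against 33.7% in Arm A at f = 0.5), because the set also sheds patients with short exposure and no CRI. That stands: fewer events are counted, but the compared proportion need not fall.

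A permanent stop may also be uncommon. The CRI definition covers infections treated with antibiotics through the catheter, exclusion criterion 3 recognises conservatively managed infection, and patients need PN regardless of the trial. At f = 0.2 the rule drops about 2 CRIs per arm with daily PN (1.96 and 1.88) and under 1 per arm at 3 days per week. That stands too, and it is why the figures are a range. The window is itself ambiguous, however. If two weeks means 14 PN days, then at 3 days per week W is 14 × 7/3 = 32.7 days, and the losses at f = 1 rise from 3.5 and 3.4 to 7.4 and 7.1.

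Sections 6.3 and 6.3.2 leave special cases and further detail to a later SAP. That could add an analysis, but as written it does not reverse a population fixed in both the objectives and the methods. Severe infections, PN-related adverse events and hospitalisations remain in the safety set. This limits the loss, but they are different endpoints: a CRI need not be grade 3, so they do not replace a comparison of CRI.

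**Conclusion.** The concern holds. The plan assigns a safety endpoint to a set whose entry condition that endpoint can prevent a patient from meeting, and it plans no CRI comparison elsewhere. This follows from the definitions and needs no assumption.

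The size does rest on assumptions. In the illustration, between under 0.5 and about 8 first CRIs per arm are lost. The between-arm ratio is almost unchanged when early stopping is alike in the arms, and is distorted by roughly 11 to 12% at the outer limit for a mean of 120 days. Neither the direction nor the presence of such a distortion can be shown from the documents. CRI is secondary with descriptive p-values, and the primary test is untouched. The point should still be settled before database lock, so that the choice of population is not made after seeing the data.

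**What to change.** In sections 5.1.2 and 6.3.2, make the main CRI comparison, for A against B and for A-1 against A-2, in the existing safety set, counting every CRI from the first home application. Keep the per-protocol CRI analysis as a sensitivity analysis. Because the safety set groups patients by treatment received, also report CRI in the same patients by randomised arm as a supporting analysis.

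The cost is a change of wording and a few extra tables. CRI is already recorded at each documented visit and at end of treatment, and adverse events up to 14 days after the last study treatment (section 9.1). The sample size of 192, or 216 with dropout, does not change. A small condition on having started home PN remains.

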#### 6.1 Sample size calculation

For the primary endpoint statistical significance is assessed using a fisher's exact test at a two-sided alpha level of 0.05 for the objective patient autonomy.

The power calculation was carried out using the Power Procedure in SAS version 9.4 (method: Walters normal approximation for unbalanced groups): Considering the 2:1 randomization, 128 patients must be included in Arm A (Standard Parenteral Nutrition using Eurotubes®) and 64 patients in Arm B (Standard Parenteral Nutrition using 2/3-chamber bags), resulting in a sample size of 192 patients, to ensure 80% power to detect an improvement of the objective patient autonomy from 5% with traditional 2/3-chamber bags to 20% with Eurotubes®.

Assuming a dropout rate of about 10% it is planned to include 216patients.

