#### **Primary Endpoint**

The primary analysis will compare patients randomized to Arm A (Standard Parenteral Nutrition using Eurotubes®) with those randomized to Arm B (Standard Parenteral Nutrition using 2/3-chamber bags) regarding the objective patient autonomy and will be based on the ITT population. To test the hypothesis:

H01: "The objective patient autonomy does not differ between the treatment Arms A and B

$$(P_{12} = P_{22})$$
."

VS.

-CONFIDENTIAL- Page 21 of 33

H11: "The objective patient autonomy differs between the treatment Arms A and B  $(P_{12} \neq P_{22})$ ."

fisher's exact test is used with a type I error of 0.05.

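### Fisher's exact test is valid and the trial is correctly sized for it, but an equally exact unconditional test would gain about 2 to 6 points of power at no cost in patients

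*Combined protocol and SAP*

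**What the plan says.** Section 6.1 states for the primary endpoint that "statistical significance is assessed using a fisher's exact test at a two-sided alpha level of 0.05". The power calculation was done in SAS, and the approximation is given as "method: Walters normal approximation for unbalanced groups". It asks for 128 patients in Arm A and, on the other side, "64 patients in Arm B (Standard Parenteral Nutrition using 2/3-chamber bags), resulting in a sample size of 192 patients". The target is 80% power if autonomy rises from 5% in Arm B to 20% in Arm A. Enrolment is raised to 216 for about 10% dropout. Section 6.3.2, Primary Endpoint, repeats that "fisher's exact test is used with a type I error of 0.05".

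For all other rates, section 6.3.2, Secondary Endpoints, says: "Rates will be compared using fisher's exact test and continuous variables using t-test". By the objectives in section 5.1.2, these include catheter-related infections, other catheter complications, grade 3-5 infections and PN-related adverse events, for A vs B and again for A-1 vs A-2. The p-values are called descriptive, with no hypothesis or significance level attached. On multiplicity the section says: "Thus, the p-values will reflect the comparison-wise error and not the experiment-wise error". It also allows a method to be modified after a suitability check and leaves details to a later SAP.

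**The concern.** Fisher's test computes its p-value conditionally on the total number of events in the two arms. This design fixes the arm sizes, approximately, but not the number of events. Conditioning leaves few attainable p-values when events are sparse, and fewest when the arms are equal, as in A-1 vs A-2. The probability of p ≤ 0.05 when the arms do not differ is then below 5%, and power falls with it. An unconditional exact test gives the same guarantee on the error and wastes less of it.

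What is at stake is efficiency: some power for the primary comparison, and more conservative p-values than necessary for the secondary and safety rates. It is most visible in the low-glucose comparison, which is the smallest and has no power calculation.

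**Working it through.** **Inputs.** From section 6.1: two-sided α = 0.05, 5% (Arm B) vs 20% (Arm A), 128/64 required, 216 enrolled. From section 4: 2:1 and then 1:1 allocation. This gives 144/72 for A vs B at full enrolment, and 64/64 (half of 128) or 72/72 (half of 144) for A-1 vs A-2. The common event rates of 3-30% and the A-1 vs A-2 contrasts below are assumptions, because the documents give no rates for the secondary endpoints.

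**Step 1: the plan's own figure.** Walters' arcsine approximation with continuity correction is

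h = arcsin√(p_A − 1/(2n_A)) − arcsin√(p_B + 1/(2n_B)), power = Φ(2h√(n_A n_B/(n_A + n_B)) − 1.960).

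- 128/64: h = 0.4587 − 0.2428 = 0.2159; 2 × 0.2159 × √(128 × 64/192) = 2.821; Φ(2.821 − 1.960) = 0.805.
- 126/63: Φ(2.794 − 1.960) = 0.798.

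So 128/64 is the smallest 2:1 design that reaches 80%, and the stated figure reproduces. For dropout, 192/0.9 = 213.3, which 216 covers. Summing over all 2×2 tables gives an exact Fisher power of 82.6% at 128/64.

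**Step 2: true size of Fisher's test.** For each table (x, y), take the two-sided Fisher p-value, which sums the tables no more probable than the one observed. Then

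size(π) = Σ Bin(x; n₁, π) · Bin(y; n₂, π) over tables with p ≤ 0.05.

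**Step 3: Boschloo's test.** Use the two-sided Fisher p-value as the test statistic. Take the largest cut-off c for which the maximum of size(π) over π is at most 0.05, and reject when the Fisher p-value is at most c. This gives c = 0.0685 (64/64), 0.0654 (72/72), 0.0580 (128/64) and 0.0570 (144/72). Every c exceeds 0.05, so the test rejects whenever Fisher's does.

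Size at nominal 5%:

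| Common rate | Fisher 64/64 | Boschloo 64/64 | Fisher 128/64 | Boschloo 128/64 |
|---|---|---|---|---|
| 3% | 0.4% | 1.4% | 2.7% | 3.0% |
| 5% | 1.2% | 2.8% | 3.1% | 3.6% |
| 10% | 2.3% | 3.5% | 3.5% | 4.3% |
| 20% | 3.0% | 4.2% | 3.9% | 4.6% |
| 30% | 3.1% | 4.5% | 4.2% | 4.8% |
| Maximum over all rates | 3.5% | 4.8% | 4.6% | 5.0% |

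The last entry is 4.96% before rounding. At full enrolment Fisher's maximum is 3.7% (72/72) and 4.3% (144/72).

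**Step 4: power** (the same sum, with a different rate in each arm).

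| Comparison | Rates | Fisher | Boschloo | Gain (points) |
|---|---|---|---|---|
| Primary, 128/64 | 5% vs 20% | 82.6% | 85.1% | 2.5 |
| Primary, 144/72 | 5% vs 20% | 88.1% | 89.9% | 1.8 |
| A-1 vs A-2, 64/64 | 5% vs 15% | 35.9% | 42.1% | 6.2 |
| A-1 vs A-2, 64/64 | 5% vs 20% | 66.8% | 71.5% | 4.7 |
| A-1 vs A-2, 64/64 | 10% vs 25% | 53.2% | 58.6% | 5.4 |
| A-1 vs A-2, 64/64 | 10% vs 30% | 76.7% | 80.8% | 4.1 |
| A-1 vs A-2, 64/64 | 20% vs 40% | 63.0% | 68.8% | 5.8 |

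For 10% vs 25%, Fisher's test needs about 71 per arm to match Boschloo's with 64.

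**Step 5: effect on a reported p-value.** With 4/64 vs 12/64 events, Fisher's p is 0.059 and Boschloo's is 0.042.

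**The case against.** The strongest defence is that nothing in the plan is broken, and most of it stands.

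- **The primary analysis is consistent.** Test and sample size match, the 80% target is exceeded, and no planned power is missing. A reader might infer that the primary comparison is underpowered; step 1 shows that it is not.
- **Secondary p-values trigger no decision.** Size and power at 5% matter fully only against a threshold, and the plan sets none. The example in step 5 straddles 0.05, a line the plan declines to use for these endpoints. What remains is that the p-values will be reported and read, and less conservative ones are more informative.
- **The comparison-wise sentence is about multiplicity.** A reader might take it as a promise that p = 0.05 means an error of exactly 5%, which Fisher's test would then break. In context it follows the statement that multiple tests are not adjusted for, and contrasts error per comparison with error over the whole trial. It makes no claim about calibration.
- **Conditioning is a legitimate choice.** Fisher's p-values never understate the error. To call them wrong would take one side of a long-standing debate.
- **The plan already allows a change of method.** That helps, but it favours settling the test now: a switch made once results are visible is open to selection.

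One part of the defence does not dispose of the point. On the plan's own criteria, two-sided 0.05 and power, a test exists that is never less powerful and controls the same error.

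**Conclusion.** This is a cheap efficiency improvement, not an error. Fisher's test is conservative here: markedly so in A-1 vs A-2 (size 0.4-3.1% at rates of 3-30%, at most 3.5% at any rate for 64/64) and modestly so in A vs B (2.7-4.2%, at most 4.6% for 128/64). Boschloo's test recovers about 2 points of primary power (2.5 at 128/64, 1.8 at 144/72) and about 4 to 6 points in the A-1 vs A-2 scenarios shown.

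The bound on Fisher's size holds for every event rate at these arm sizes. The 3-30% range and the A-1 vs A-2 power figures rest on assumed rates, and the per-protocol and safety sets may be smaller than the arm sizes used.

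A reader might go further and infer that the plan hides harm in the low-glucose arm. The documents do not support that: no safety conclusion is tied to a p-value threshold, confidence intervals are among the planned summaries, and no power is claimed for A-1 vs A-2. Nor does the change cure sparse data. At a 3% event rate and 64/64, Boschloo's size is still only 1.4%.

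**What to change.** Before any analysis, in section 6.3.2 (or the SAP to which it defers), replace Fisher's exact test for the secondary and safety rates with Boschloo's unconditional exact test. State the version: two-sided, with the two-sided Fisher p-value as the statistic, and the p-value maximised over the common event rate. The version matters in the 2:1 comparison, where doubling a one-sided p-value is a different test that does not always reject when Fisher's does. Keep the secondary p-values descriptive.

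If the primary test stays unstratified, make the same change in sections 6.1 and 6.3.2 for the primary endpoint. The 192 evaluable and 216 enrolled patients remain valid, because the new test is never less powerful at the same two-sided 0.05.

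The cost is a wording change and a checked software routine, with no extra patients or data. The drawback is a less familiar test whose two-sided definition must be written out.

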# **Arm A-2**: Standard Parenteral Nutrition using Eurotubes®.

Patients randomized to Arm A and in a second randomization to treatment Arm A-2 will receive standard PN in Eurotubes®.

Patients will be recruited during regular consultation visits.

An overview of the study scheme is given in Figure 1.

-CONFIDENTIAL- Page 14 of 33

[figure not shown]

Figure 1: Study Scheme.

-CONFIDENTIAL-

At screening and at all regular visits during the HPN treatment period (one visit per four-week interval after randomization for a maximum of 12 months) the ECOG performance status and body weight will be determined. Additionally, physical examinations and laboratory assessments including CRP, albumin and total protein levels will be performed. Laboratory assessments do not need to be repeated at screening if laboratory assessments were done prior to screening within clinical routine and results are not older than 2 weeks. The type of catheter used for parenteral nutrition will be documented (Port-a-Cath, Hickmann/Broviac catheter etc).

The HPN therapy and any modifications and adjustments to this plan during the course of HPN treatment will be recorded from visit 1 onwards.

Anti-cancer treatment at the time of screening and any changes during the course of the HPN treatment period (e.g. type of treatment) will be documented.

Monitoring of Adverse Events and medical device deficiencies will be performed at every visit. AEs will be graded according to the National Cancer Institute's Common Terminology Criteria for Adverse Events (NCI CTCAE) version 5.0.

During the study the patient will maintain a study diary to document details of the administration of the HPN. A QoL questionnaire will be completed during regular study visits until EOT.

After completion of study treatment, patients will enter the follow-up period. During this period, they will be followed approximately every 3 months for survival which can be done by phone.

-CONFIDENTIAL- Page 16 of 33

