#### 5.2.2 Secondary endpoints

#### Efficacy endpoints

- Relative weight change determined at baseline and during study visits approx. every four weeks after enrolment;
- Relative change of albumin and CRP levels measured at baseline and during regular study visits;
- Overall survival (OS) defined as the time from randomization to death from any cause.

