#### 6.3.2 Statistical methods for the analysis

#### Patient Demographics/Other Baseline Characteristics

The following demographic and baseline characteristics will be summarized descriptively by treatment group:

- Gender and age;
- Patients' disease (e.g. colon cancer, breast cancer, gastric cancer);
- Tumor status (localized or metastatic solid tumors);
- Number and type of organs involved in metastatic disease (e.g. liver, lung, lymph nodes, bone);
- Patients history (concomitant disease, number and type of previous anti-cancer therapies);
- Type and start date of the current/concomitant anti-cancer therapy;
- ECOG performance status;
- mGPS
- Nutrition risk screening score;
- Baseline lab values and baseline QoL;
- Other characteristics.
- Type of central catheter used for parenteral nutrition

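### Albumin relative change is tested without baseline adjustment, which costs precision; for CRP, whether a log-scale adjusted analysis gains or loses depends on skew and effect shape

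*Combined protocol and SAP*

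**What the plan says.** Section 5.2.2 defines the endpoint as "Relative change of albumin and CRP levels measured at baseline and during regular study visits". Section 6.3.2, Secondary Endpoints, compares "continuous variables using t-test" and names no covariate, stratification factor or transformation for these variables. It also does not say at which visit the arms are compared.

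The baseline values exist. Section 4 states that at screening and at the regular visits "laboratory assessments including CRP, albumin and total protein levels will be performed", Table 1 repeats this, and section 6.3.2 lists "Baseline lab values and baseline QoL" among the characteristics tabulated by treatment group.

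The same section limits the inferential weight: "The parameters will be evaluated in an explorative manner", and "All resulting p-values for secondary endpoints will be considered descriptive". It holds that its methods "are suited for the data and distributions usually expected in this type of trials", and adds a safeguard: "The suitability will be checked and if necessary, the statistical method will be modified accordingly, with critical discussion of the original and modified results". Remaining specifics are left to the statistical analysis plan, to be settled before database lock. Section 5.1.2 names albumin and CRP as efficacy measures both in the general list and for Arm A-1 vs A-2.

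**The concern.** Dividing by baseline is not the same as adjusting for it. When baseline and follow-up are imperfectly correlated, a change score carries the noise of both measurements, while a model with baseline as covariate removes the predictable part. Randomisation keeps the unadjusted comparison fair, so the cost is wider confidence intervals, not a wrong answer.

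The suitability check does not clearly close this gap. It concerns data and distributions. Albumin that looks roughly normal would pass it and stay unadjusted, and a rank test would recover nothing. At stake is the precision of two named efficacy comparisons, most noticeably A-1 vs A-2, with about 64 patients per arm.

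CRP differs. If it is right-skewed, relative change has a long upper tail, and a log scale looks attractive. Whether it helps depends on where in the distribution the treatment acts.

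**Working it through.** **Inputs.** Arm sizes of 128 and 64 come from section 6.1. That figure reproduces: the Walters approximation for 5% vs 20% gives 80.5% power at 64/128 and 79.8% at 63/126. The documents give no figure for albumin or CRP, so every SD, correlation r and effect below is an assumption. Two-sided 0.05 is used only as a yardstick. All patients are taken to contribute at one visit, and the stratification factors were not simulated.

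**Validity.** With no true difference, the t-test on relative change rejected in 3.4 to 5.7% of simulated trials for CRP, and in 5.0 to 5.6% for albumin.

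**Baseline adjustment in general.** For absolute or log change the variance is 2σ²(1−r). For ANCOVA it is σ²(1−r²). The ratio is (1−r²)/[2(1−r)] = (1+r)/2, so the efficiency of the unadjusted change is 65%, 75% and 85% at r = 0.3, 0.5 and 0.7, whatever the SD.

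**Albumin** (assumed normal, mean 35, SD 5.5, difference 1.5 g/L, 128 vs 64; simulated power):

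| r | t-test, relative change | relative change, baseline as covariate | ANCOVA on follow-up value |
|---|---|---|---|
| 0.5 | 41% | 52% | 54% |
| 0.7 | 60% | 68% | 70% |
| 0.8 | 78% | 83% | 85% |

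Closed-form check of the last column at r = 0.5: √(1/128 + 1/64) = 0.1531; z = 1.5/(5.5 × √0.75 × 0.1531) = 1.5/0.7292 = 2.057; power = Φ(2.057 − 1.960) = 53.9%.

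Keeping the endpoint of section 5.2.2 and adding baseline gains 11, 8 and 5 points. Moving to the follow-up value adds 2 points in each row, which is the part due to leaving the ratio. A rank test on relative change had the same power as the t-test.

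**CRP, uniform proportional reduction** (assumed lognormal with log-SD s). The efficiency of the t-test on relative change against log-scale ANCOVA is s²(1−r²)/[exp(2s²(1−r))−1].
- s = 1.1, r = 0.5: 1.21 × 0.75/(e^1.21 − 1) = 0.9075/2.3535 = 0.386.
- s = 0.5, r = 0.5: 0.1875/0.2840 = 0.660.
- Power for a 30% reduction at s = 1.1, r = 0.5: 40 to 42% for the t-test over repeated runs, 54% for a rank test, 68 to 69% for log-scale ANCOVA. At s = 0.5 the t-test and ANCOVA reach 99% and 100%.
- Adding untransformed baseline CRP to a model of relative change cuts the variance by only 0 to 10% (s 0.8 to 1.2), so in this setting the gain comes from the log scale with log baseline.

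**CRP, effect confined to infections** (assumed 8-fold rise in infected patients, r = 0.5, 128 vs 64; power for t-test on relative change / log-scale ANCOVA):

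| Infected, A vs B | s = 0.5 | s = 0.8 | s = 1.1 |
|---|---|---|---|
| 2% vs 12% | 67/55% | 52/38% | 34/27% |
| 5% vs 15% | 52/48% | 39/33% | 28/24% |

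Here the planned test is ahead in every cell, because the log scale compresses the upper tail in which the effect lies.

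**The case against.** The strongest case against has four parts.

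- **The CRP gain assumes a convenient effect.** Sections 3.5 and 3.6 expect Eurotubes to bring fewer complications and to prevent catheter infections, which would affect a minority of patients. Under that shape the planned t-test does better. This stands. A reader might infer that log-scale ANCOVA should replace the CRP test because it is generally more precise; the documents give neither the distribution nor the effect shape needed to support that.
- **Part of the albumin gain comes from dropping the ratio.** In a separate simulation at r = 0.8, the t-test on relative change, the t-test on absolute change and ANCOVA had 76.4%, 79.2% and 83.3% power, so 2.8 of the 6.9 points come from the ratio. This stands as a small correction: with baseline in the model and relative change kept, most of the gain remains.
- **The analysis plan may still add adjustment.** Section 6.3.2 defers details and allows a change of method, so its silence is not a decision against a covariate. This is fair, and the clause may well deal with skew in CRP. But the one method stated is the t-test, and nothing commits to baseline adjustment.
- **The analyses are explorative.** Power at 0.05 is not a criterion the plan uses for them. Agreed; it stands here for the width of the intervals.

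**Conclusion.** A minor point that holds firmly for albumin and only conditionally for CRP.

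For albumin, the unadjusted comparison gives up 5 to 11 points on the power yardstick against the same endpoint with baseline as covariate, and 7 to 13 points against ANCOVA on the follow-up value. This rests on the assumed mean, SD and difference, r of 0.5 to 0.8, and complete data at 128 vs 64. Deaths and dropout will lower the numbers at later visits. The direction of the gain does not depend on the particular SD.

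For CRP, a log-scale adjusted analysis is a trade-off: ahead for a uniform shift in skewed data, behind for an effect limited to infected patients.

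A reader might also infer that the planned test is invalid or produces false differences between arms. It does not: its type I error is near nominal. The primary endpoint and its sample size are untouched.

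**What to change.** In section 6.3.2 and the statistical analysis plan:

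- **Albumin.** Analyse each documented visit, with one named in advance as the main visit, by ANCOVA with baseline albumin, arm and the stratification factors of section 4 (ECOG, mGPS, concurrent systemic anti-cancer treatment). Report the estimate with a 95% CI. Use either relative change as the outcome, which keeps the section 5.2.2 endpoint, or the follow-up value, with relative change then kept as a descriptive table.
- **CRP.** Keep the planned comparison of relative change. Beside it, prespecify an ANCOVA of log follow-up CRP on log baseline CRP, arm and the same factors, reported as a geometric mean ratio with 95% CI. Make no claim that it is generally the more precise of the two.

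The cost is a few sentences and routine programming, with no new data or visits. If the follow-up value is chosen for albumin, the estimate becomes an adjusted mean difference instead of a difference in relative change, and the text should say so. For CRP, two analyses answer somewhat different questions and may disagree, so both should be reported.
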